# 5.4. Subject Identification and Allocation to Treatment

#### **5.4.1.** Subject Identification

Initials, year of birth, and age of subjects who have signed the ICF to begin Screening procedures will be collected in the source data for verification purpose. At Screening – Part 1 Visit, a unique identification number will be assigned by the interactive response technology (IRT). Any subject records or dataset that are transferred to the Sponsor will contain the identifier only; subject names, initials, date of birth, or any information which would make the subject identifiable will not be transferred.

In the rare circumstance where a subject is entered into the treatment part of the study, but does not receive the first dose of study drug, the Study Coordinator/Research Nurse must immediately inform the Clinical Research Associate (CRA) that the study drug was not administered.

#### **5.4.2.** Treatment Allocation

All subjects will be randomized to receive double-blind treatment consisting of either ALZ-801 265mg or placebo in a 1:1 ratio. Randomization will be stratified by use of concomitant AD medications (AChEI or none), age (50 through 65 years or > 65 years at the Screening – Part 1 Visit, gender, and disease stage (MMSE  $\leq$  26 or > 26 at the Baseline Visit). It is expected that

Confidential Page 50 of 115

approximately 60% will be AD subjects with MMSE 22-26 (inclusive), and approximately 40% will be AD subjects with MMSE 27-30 (inclusive). Double-blind treatment will be dispensed in blister cards.

# 5.5. Subject Withdrawal, Termination, and Replacement

Study subjects may discontinue from the study or be withdrawn from the study for any of the following reasons:

- At the subject's or the subject's legally authorized representative with the subject's assent request for any reason (withdrawal of consent)
- Subject whose cognitive function declines and is deemed by the Investigator to be unable to provide assent/consent for continuation in the study
- At the discretion of the Investigator, if deemed appropriate, for any reason
- At the discretion of the Sponsor, if deemed appropriate, for any reason
- Subject for whom investigator deems initiation of memantine medically necessary must be withdrawn
- Subject noncompliance: If a subject takes less than 70% of study drug tablets, this may be considered reason for withdrawal, by Investigator or Sponsor request
- Protocol violation that compromises subject safety
- For safety concerns; medically significant AE(s) or SAE(s) with CTCAE > Grade 3 may be considered reason for withdrawal, if appropriate in the judgment of the Investigator
- Subject who becomes pregnant must be withdrawn from the study
- The subject's caregiver/study partner is no longer willing or able to participate in the study and a suitable replacement caregiver/study partner cannot be found
- Brain MRI findings: subject who has any of the following findings on central reading:
  - o Macrohemorrhage: defined as hemorrhage with size > 1 cm^3
  - o ARIA-E (vasogenic edema) associated with neurologic symptoms: dosing will be halted for 1 month and MRI repeated. Resumption of dosing may be considered after discussion between Investigator and Sponsor's medical officer.
- Subject who experiences an event of syncope without a clear triggering event (e.g., blood draw or pain inducing a vasovagal episode) will be withdrawn from the study
- Subject with clinically notable ECG abnormalities based on the average of triplicate ECG readings. The criteria for clinically notable or significant ECG results that require subject withdrawal are as follows:
  - o QTcF (Fridericia's correction) interval > 500 msec, and
  - An increase in QTcF interval of > 60 msec from baseline.

Confidential Page 51 of 115

**Note:** The criteria for QTcF are based on the upper threshold in elderly subjects who are known to have higher ULN [Reardon & Malik, 1996], and is the threshold commonly used in AD studies.

- Subject with confirmed clinically notable changes in liver function tests (LFT) may be withdrawn from the study. The criteria for abnormal LFTs are as follows:
  - $\circ$  ALT or AST  $> 8 \times ULN$ ,
  - $\circ$  ALT or AST  $> 5 \times$  ULN for more than 2 weeks, or
  - o ALT or AST  $> 3 \times$  ULN, and TBL  $> 2 \times$  ULN or PT  $> 1.5 \times$  ULN
- Weight loss: Subjects who are not intentionally dieting who show the following degree of weight loss on study drug:
  - $\circ$  Weight loss > 6% of body weight compared to baseline, and
  - Reaching BMI < 22 if  $\ge$  65 years of age; or
  - o Reaching BMI < 16 if < 65 years of age

**Note**: The ideal body weight and BMI cut-off criteria for those < 65 years of age or  $\ge 65$  years of age are based on a meta-analysis by Winter et al. (2017).

The reason for discontinuation must be recorded on the appropriate page of the electronic case report form (eCRF).

## **Early Termination**

Should a study subject request or decide to withdraw or is withdrawn by Investigator or Sponsor, an Early Termination (ET) Visit will be conducted at the time of discontinuation. All efforts should be made to conduct assessments and to complete and report observations as thoroughly as possible up to the date of withdrawal, including all the evaluations shown in the Schedule of Assessments [Appendix 2]. All information will be reported on the applicable pages of the eCRF.

If the subject withdraws from the study due to an AE, every reasonable attempt should be made to follow the subject until the AE resolves or until the Investigator, after discussion with the Sponsor, deems the AE to be chronic or stable. All SAEs will continue to be followed for 4 weeks after the ET visit or until the AE is deemed to be either chronic or stable.

#### Subject Replacement

If drop-out rate is more than projected (approximately 18%), subjects including those in the CSF sub-study who drop out may be replaced after discussion with the Safety Management Committee (SMC).

#### 6. INVESTIGATIONAL MEDICINAL PRODUCT

# 6.1. Investigational Medicinal Product and Control Description

The investigational medicinal product (IMP) will be 265mg ALZ-801 (provided as  $1 \times 265$ mg tablets) or matching placebo ( $1 \times$  placebo tablets [size- and color-matched to ALZ-801]).

Confidential Page 52 of 115

All subjects will receive study drug, one tablet BID, taken with a morning and evening meal (or within 30 minutes after each meal) with approximately 10 to 12 hours between doses. Subjects in the placebo treatment arm will receive placebo tablets BID throughout the study. Subjects in the active treatment arm will receive placebo in the morning and a 265mg tablet of ALZ-801 in the evening during the first two weeks of the study; thereafter, they will receive a 265mg tablet BID.

On clinic visit days, only one dose of study drug will be taken from one of the newly dispensed blister cards and administered at the study site.

## 6.1.1. Formulation, Appearance, Packaging, Labeling, and Shipping

#### **Formulation**

The ALZ-801 tablet consists of ALZ-801 drug substance, microcrystalline cellulose, silica colloidal anhydrous (Aerosil 200), PVP VA 64 (copovidone) and magnesium stearate. ALZ-801 tablets are coated with Opadry II White. Each tablet contains 265mg of ALZ-801 drug substance.

Placebo tablets contain all of the same excipients as ALZ-801 tablets, but do not contain any ALZ-801. ALZ-801 and placebo used for the tablets are manufactured under cGMP and meet specifications for clinical use.

#### **Appearance**

ALZ-801 is provided as white, oval-shaped, immediate release tablets [Figure 7].

Figure 7 Appearance of ALZ-801 and Matching Placebo Tablets

#### **Packaging**

ALZ-801 immediate-release tablets will be packaged as kits containing blister cards. Each blister card contains a 1-week supply with two blister strips, one for AM and one for PM dosing (8 tablets in each strip). The total number of tablets for a 1-week blister card is 16 tablets, for 7 days of dosing plus 1 day overage. The materials used for the blister strips are of standard commercial grade. The product contact side of this material conforms to FDA 21CFR175.300 and the Council of Europe Resolution AP (2004) and (EU) No. 10/2011.

Confidential Page 53 of 115

## Labeling

Representative label is shown below in [Figure 8].

#### Figure 8 Representative Label of Drug Product

## ALZ-801 265 MG Protocol code: ALZ-801-AD301

#### FOR CLINICAL TRIAL USE ONLY

Each blister card contains a 1-week supply with two blister strips (8 tablets in each strip) for AM and PM dosage of ALZ-801 immediate release tablets or placebo. The total number of tablets for a 1-week blister card is 16 tablets.

Kit Number:

Site Number: Batch Number: Patient Number: Investigator:

Date of dispensation: Expiry date: MMM/YYYY

#### **Dosing schedule:**

Orally, twice per day, approximately 10-12 hours apart. Tablets shall be taken with a full meal or within 30 minutes after a full meal.

On clinic visit days, only one dose of study drug will be taken from one of the newly dispensed blister cards and administered at the study site.

Use only according to study physician's instructions.

Store at room temperature (15-25 °C).

Caution: NEW DRUG- Limited by Federal (U.S.A.) law to investigational use only.

# Shipping

Study drug will be shipped directly to the pharmacist or study coordinator/research nurse at the study site after all required regulatory and legal documents have been received by the Sponsor or its designee. Upon receipt of the study drug shipment, the pharmacist or study coordinator/research nurse will verify the condition of the study supplies, register the study drug, and document per instructions provided.

Instructions for resupply shipments or replacement of study drug are provided in the IRT Manual.

#### 6.1.2. Product Storage and Stability

IMP must be stored in a limited access area at room temperature (15°C to 25°C or 59°F to 77°F). Only authorized study personnel may access the study drug according to local and national regulations.

#### 6.1.3. Replacement Procedures for Investigational Medicinal Product

Instructions to resupply shipments or replacement of study drug are provided in the IRT Manual.

Confidential Page 54 of 115

# 6.2. Dosing and Administration, and Adjustment

### 6.2.1. Dosing Regimen

Study drug will be administered as an oral tablet beginning at the Baseline Visit (Day 1). The first dose of study drug will be administered in the clinic and must be administered to the study subject **only after** all pre-dose assessments (including the blood draw) are performed.

The dosing regimen is one tablet orally BID except on clinic days when one tablet only will be administered at the study site. In the initial 2-week titration period, the active treatment group will receive placebo in the morning and ALZ-801 in the evening. Thereafter, ALZ-801 will be administered in the morning and evening. In the placebo group, subjects will always receive placebo in the morning and evening throughout the study. The last dose of study drug will be administered at the clinic on the morning of the Week 78 visit.

The study drug should be taken with a full meal or within 30 minutes after a full meal (breakfast or dinner) with approximately 10 to 12 hours between doses. On days of clinic visits, dosing of study drug for the day will occur once and will be administered by the site staff at the site. The times of study drug administration the night prior to clinic visit and when taken at the study site will be recorded.

# 6.2.2. Dose Adjustments/Modifications/Delays

Dosage adjustments or down titration will not be allowed for ALZ-801 throughout the study except for the dose change on Day 15 after the titration period.

No gradual reduction in medication is required for withdrawal from the study. If for any reason, a subject misses one or more doses of study drug, he/she should resume the regular dosing regimen, unless informed otherwise. The interruption in study drug dosing should be reported and recorded.

# 6.3. Study Drug Accountability

It is the responsibility of the Investigator to supervise accurate monitoring of the receipt, storage, dispensing, and accounting of all study drug according to accepted medical and pharmaceutical practice. Copies of all shipment records of study drug shipments must be retained. Accurate, original site records of study drug inventory and dispensing must be maintained using the forms provided or using the form the site pharmacy maintains, if they are approved for use by the Sponsor or designee.

All study drug documentation must be maintained by the Pharmacist or dispenser. All disposition records must be made available for inspection by the Sponsor or their designee, upon request.

Drug accountability forms will be provided for the accounting of study drug at the subject level and for the overall study inventory. A reason(s) must be provided for any tablets that are not accounted for.

Only subjects enrolled in the study may receive study drug and only authorized study site personnel may supply or administer the drug. Only study drug with appropriate expiry dates may be dispensed.

Study subjects will be instructed to return all dispensed study drug blister cards to the study site at each visit. Blister cards dispensed at the previous visit will be collected, and the Pharmacist or

Confidential Page 55 of 115

designee at the site will inspect all returned blister cards, as well as record the number of used and unused tablets on the drug accountability log. Each site must keep all used and unused blister cards until the CRA either arranges return to the distribution center or gives instruction for their disposal. If unused tablets remain at the end of the study, they will be accounted for at the site close-out visit in the presence of the CRA, who will provide instructions for study drug disposal.

# 6.4. Study Drug Compliance

All subjects in this study will commence therapy onsite on Day 1 (Baseline); oral study drug will be administered under clinic staff supervision. After subjects are discharged to continue therapy at home, subjects and their caregivers/study partners should be counseled on the need to meet 100% compliance with study drug. The Investigator or designee should ensure that subjects meet this goal throughout the study period. Compliance will be assessed on subsequent visits by returned tablet count. Administration of investigational product and any deviation(s) from the prescribed dosage regimen should be recorded.

#### 7. STUDY PROCEDURES AND SCHEDULE

# 7.1. Study Specific Procedures/Evaluations

All study procedures and evaluations will be completed according to the Schedule of Assessments as shown in [Appendix 2]. Every effort should be made to complete the required procedures and evaluations at the designated visits and times.

#### 7.1.1. Remote Visits

Coronavirus disease 2019 (COVID-19) has significantly impacted study subjects' ability to attend study visits due to government-ordered lockdowns or the closure of state (domestic) and/or national borders and may continue to do so.

Protocol deviations, urgent safety measures, and modifications to this protocol might be necessary to prioritize and ensure the safety of trial participants, their families, and study site teams, and maintain the integrity of the study. All measures and actions that may be implemented due to COVID-19 will be reviewed by the Data and Safety Monitoring Board (DSMB), Medical Monitor, and applicable Principal Investigators.

For any skipped in-person visits based on the availability of the patient/ the study team, within approximately  $\pm$  3 days of the originally scheduled visit, the study team should contact the subject (and as applicable, their caregiver/study partner/legal representative) via phone/telemedicine to collect information in order to monitor AEs or SAEs, and provide study oversight (hereafter referred to as "remote visits").

Protocol deviations related to COVID-19 will be documented. These deviations in protocol-specific procedures due to COVID-19 (changes in study visit schedules, remote and/or missed visits, or patient discontinuations) may lead to missing information.

For each patient, the eCRF will capture specific information that (as much as possible) explains the basis of the missing data, including the relationship to COVID-19 for missing

Confidential Page 56 of 115

protocol-specified information (e.g., from missed study visits or study discontinuations due to COVID-19).

#### 7.1.2. Informed Consent

At Screening – Part 1 Visit, prior to stated procedures (APOE genotyping, MMSE, demographics, medical history and prohibited medications) are performed, the site staff will obtain the signed ICF from each subject or the subject's legally authorized representative with the subject's assent. Complete signed ICF from subject and caregiver/study partner will be obtained prior to any other procedures at the Screening – Part 2 Visit or at the Screening – Part 1 Visit if APOE4/4 status is known or confirmed using a rapid genotype test.

## 7.1.3. Prohibited Medications

The list of prohibited medications starting at the Screening – Part 1 Visit and at all times during the study is provided in [Table 1].

#### 7.1.4. Permitted Medications

During the study, any concomitant medications deemed appropriate by the Investigator to treat the subject's medical condition may be prescribed, excluding those that are prohibited. Refer to [Table 1], which also lists the exceptions to prohibited medications.

Change in dose of any permitted medications during the study period is discouraged.

All concomitant medication usage will be recorded during each study visit.

#### 7.1.5. **APOE** Genotyping

A blood sample for APOE genotyping will be required at the Screening – Part 1 Visit as shown in the Schedule of Assessments [Appendix 2]. Previous evidence of APOE4/4 status may be used as a reference and allow subjects to combine Screening – Part 1 Visit and Screening – Part 2 Visit together at the same day if the site and subject prefer.

Result from the central laboratory blood test of APOE4/4 status must be available prior to randomization.

The blood sample may be stored, with subject consent, for possible future analysis with core AD-related biomarkers, such as p-tau217, A $\beta$ 40, and A $\beta$ 42 as well as NfL and GFAP. Consent for use of this sample for possible future analysis with core AD-related biomarkers is optional.

#### 7.1.6. Future Potential Genomic Testing

A blood sample for future potential genomic testing will be requested at the Screening – Part 2 Visit as shown in the Schedule of Assessments [Appendix 2]. Consent for the collection and use of this sample is not required for study participation.

#### 7.1.7. Subject Demographics and Medical History

At the Screening – Part 1 Visit, the subject's demographics and medical history will be obtained. The demographics should include, but not be limited to, age, race, ethnicity, and gender. The medical history should include, but will not be limited to, the subject's clinically significant and relevant medical history of the following body systems: head, eyes, ears, nose, and throat;

Confidential Page 57 of 115

neurological; endocrine; dermatological; cardiovascular; respiratory; GI; genitourinary; musculoskeletal; hematological; hepatic; renal; and immunological systems.

#### 7.1.8. Prior and Concomitant Medications

Prior medications and past treatment(s) taken within the last 24 weeks prior to the Baseline Visit, as well as ongoing medications taken before the administration of the first dose of study drug, will be recorded.

A concomitant medication is defined as any medication that is taken after administration of the first dose of study drug (i.e., after receiving study drug at the Baseline Visit). Any use of concomitant medications will be recorded. During the study, initiation of or change in concomitant medications to treat an AE will also be recorded.

#### 7.1.9. Subject Eligibility

At both the Screening – Part 2 and Baseline Visits (prior to dosing), the site staff will be responsible for reviewing the inclusion and exclusion criteria to determine the subject's eligibility for the study.

#### 7.1.10. Safety Assessments

#### 7.1.10.1. Assessment of Adverse Events

AEs will be recorded beginning after signing the ICF at the Screening – Part 1 Visit until completion of the study or the final Follow-up Visit, whichever is later. AEs will be evaluated by the Investigator for severity (using CTCAE version 5.0; National Cancer Institute 2018), seriousness, and attributability to study medication. Further details on AEs, including definitions, elicitation, and reporting are provided in [Section 8].

AEs that occur before receiving study drug at the Baseline Visit will be captured as non-treatment emergent AEs. Treatment-Emergent AEs are those that occur anytime after subject has received first dose of study drug at the Baseline Visit and until the end of the Safety follow up visit or the Early Termination Visit.

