#### 7.2.14. Early Termination Visit

Early Termination is also considered an EOT visit. An ET Visit should be completed if a study subject discontinues prematurely from the study, or is discontinued from the study by the Investigator [see Section 5.5].

If a study subject prematurely discontinues from study treatment, an ET Visit should be conducted at the time of discontinuation. Every effort should be made to conduct all ET procedures as specified below and in the Schedule of Assessments [Appendix 2]. Every attempt should be made to follow study subjects who have an SAE for 4 weeks after their ET Visit. For subjects who continue to be followed for safety, SAEs should continue to be reported as described in [Section 8.4.2].

The following procedures will be performed. The recommended order is shown below:

- Vital signs (prior to blood draw)
- Physical examination
- Neurological examination
- Weight
- AE assessment
- Change in medications since last visit
- ADAS-Cog
- MMSE
- A-IADL
- CDR
- DAD
- NPI
- QoL-AD
- RUD Lite
- C-SSRS
- Single 12-lead ECG (triplicate if QTc prolongation observed previously or in current visit)
- Safety laboratory tests
- Plasma sample collection for biomarker assessment (exact time of sampling will be recorded)
- Plasma sample collection for PK assessment (exact time will be recorded)
- Urine for urinalysis
- Urine pregnancy test (female subjects of childbearing potential)
- Study drug dosing from the last dose prior to the visit (time of dosing will be recorded)

Confidential Page 78 of 115

- Study drug return, accountability, and compliance
- BP and pulse approximately 15 minutes after last blood draw
- MRI (as soon as possible, no later than 2 weeks after the ET visit)

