#### For subjects in the CSF sub-study:

- MRI should be performed and results available prior to LP.
- LPs should be performed via gravity drip method with atraumatic needles to reduce the risk of CSF leakage and post-LP headaches. This technique will allow for optimal biomarker collection and analysis.
- Site should schedule the LP as soon as possible, no later than 2 weeks after the MRI.
- CSF sample collection for biomarker assessment (exact time will be recorded)
- CSF sample collection for PK assessment (exact time will be recorded)

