#### 7.2.15. Retrieved Dropout Visit

In addition to the ET visit, subjects who discontinue the study drug during the trial will be encouraged to remain in the study (off study drug) for continued RDO visits by attending Week 52 (if applicable) and Week 78 (EOT) visits. The RDO visits will include the following procedures, in the recommended order shown below:

- Vital signs
- AE assessment
- Change in medications since last visit
- ADAS-Cog
- A-IADL
- MMSE
- NPI

For subjects who prematurely withdraw from the study,, they will be encouraged to return at Week 78 to finish study-related procedures.

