#### 8.1.1. Definition of Adverse Event (AE)

**Adverse Event**: An AE is any untoward medical event that occurs in a subject or clinical investigation subject administered a pharmaceutical product, and which does not necessarily have to have a causal relationship with this treatment. An AE can therefore be any unfavorable and unintended sign (including clinically significant abnormal laboratory findings), symptom, or disease temporally associated with the use of an investigational product, whether or not considered related to the product. Examples include the following:

- Any treatment-emergent signs and symptoms (events that are marked by a change from the subject's baseline/entry status [e.g., an increase in severity or frequency of pre-existing abnormality or disorder]);
- All reactions from study drug, abuse of drug, withdrawal phenomena, sensitivity, or toxicity to study drug;
- Apparently unrelated illnesses;
- Injury or accidents;
- Exacerbations of the underlying disease (indication);
- Extensions or exacerbations of symptomatology, subjective events reported by the study subject, new clinically significant abnormalities in clinical laboratory, physiological testing, or physical examination.

The following is not considered an AE:

- Elective procedure unless related to the AD diagnosis
- Pre-existing conditions found as a result of screening procedures

**Treatment-emergent Adverse Event:** A TEAE is defined as any new AE that begins, or any preexisting condition that worsens in severity, after at least one dose of study treatment has been administered.

Confidential Page 80 of 115

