#### 10.10.1. Adverse Events

For data summarization, AEs will be classified into standard terminology using the Medical Dictionary for Regulatory Activities (MedDRA), and reported by system organ class and preferred term.

TEAEs are defined as AEs that either started or worsened after administration of the first dose of study drug.

The number and percentage of the following types of AEs will be reported:

- TEAEs;
- TEAEs that led to study discontinuation;
- TEAEs related to study drug;
- TEAEs by maximum severity;
- SAEs; and
- SAEs related to study drug.

A listing of AEs will also be compiled.

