8.5.2 Adverse Events

Adverse event tables will include summaries of TEAEs by treatment arms. A TEAE is defined as any new AE that begins, or any preexisting condition that worsens in severity, after at least one dose of study treatment has been administered.

An overview table containing the number and percent of the following will be included and presented by treatment arms:

- Number of total AEs, TEAEs, and deaths
- Incidence of patients with at least one TEAE, drug-related TEAE, serious AE (SAE), drug-related SAE, and non-serious TEAEs
- Incidence of patients who discontinued due to TEAE, drug-related TEAE, SAE, and drug-related SAE
- Incidence of deaths and deaths due to drug-related TEAE

The following tabular summaries of TEAEs will be provided by treatment arms:

- TEAEs summarized by SOC and PT, descending frequency of PT, by maximum severity, by age group (50-65 inclusive, > 65 years), and by disease stage (MCI, Mild AD).
- Adverse events leading to discontinuation summarized by SOC and PT, and by descending frequency of PT.
- Drug-related AEs summarized by SOC and PT, and by descending frequency of PT.
- Serious adverse events summarized by SOC and PT, descending frequency of PT, and will include a summary of drug related events.
- SAE will also be summarized by age groups and by disease stage (as defined above).

MRI Safety Analsyes

The safety assessments will also include analyses of MRI findings (ARIA-E and ARIA-H) based on the central MRI readings by treatment arms.

Below are the rules to follow for AE summaries:

- A drug-related AE is defined as an AE with an assigned relationship of "possibly related," "probably related," "definitely related," or missing.
- When assessing severity, the TEAE with the worst severity will be chosen for a subject.
- AEs with missing severity will be summarized and presented separately.

AEs will be coded using most current Medical Dictionary for Regulatory Activities (MedDRA) version.

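### The TEAE definition used for the safety tables has no off-drug end, so adverse events starting long after the last dose count as treatment-emergent when a retrieved dropout attends an optional visit

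*Protocol*

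**What the plan says.** Four places define a treatment-emergent adverse event (TEAE), and only one gives an end.

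- Protocol 7.1.10.1: from the first dose "until the end of the Safety follow up visit or the Early Termination Visit".
- Protocol 8.1.1: "A TEAE is defined as any new AE that begins", or a pre-existing condition that worsens, after at least one dose. No end.
- Protocol 10.10.1, the analysis section: "TEAEs are defined as AEs that either started or worsened after administration of the first dose of study drug". No end.
- SAP 8.5.2 repeats 8.1.1: a new AE, or "any preexisting condition that worsens in severity, after at least one dose of study treatment has been administered". No end.

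The visits around treatment discontinuation matter here. Under Protocol 7.2.14, when a subject stops study drug early, "an ET Visit should be conducted at the time of discontinuation". The early-termination (ET) MRI is then due "as soon as possible, no later than 2 weeks after the ET visit". For the CSF sub-study the same section adds: "Site should schedule the LP as soon as possible, no later than 2 weeks after the MRI". Under Protocol 7.2.15, "subjects who discontinue the study drug during the trial will be encouraged to remain in the study (off study drug) for continued RDO visits" at Week 52 (if applicable) and Week 78, and AE assessment is a listed procedure at those visits.

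AE recording does not close at the ET Visit. Protocol 7.1.10.1 runs it to study completion or the final follow-up visit, whichever is later, and 8.4.1 runs it to the Safety Follow-up Visit.

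**The concern.** The SAP's TEAE tables have a start rule and no off-drug limit. An early stopper who accepts RDO visits can add events that began many months after the last dose. One who declines has no scheduled contact at which a new event would be picked up. The same late event also gets a different label under Protocol 7.1.10.1 than under the other three definitions.

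Safety and tolerability over 78 weeks is listed under the primary clinical objective, and the main safety tables are counts and percentages of TEAEs by arm. If early stopping or RDO return differs between arms, part of any difference in those percentages reflects off-drug follow-up rather than drug exposure.

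**Working it through.** The plan states no figure on this point, so there is none to reproduce.

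**Inputs from the documents.** Nominal days: Week 6 = 43, Week 26 = 183, Week 39 = 274, Week 52 = 365, Week 65 = 456, Week 78 = 547, Safety Follow-up = 574 (Protocol 7.2). Dropout 17% (Protocol 10.3.1). Randomized 325 (SAP 4.1).

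**Subjects concerned.** 0.17 × 325 = 55.25, about 55, and fewer in practice because RDO visits are voluntary.

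**Off-drug days at the RDO visit** (visit day minus stop day, taking the last dose and the ET Visit as the same day):

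| Stop | Seen at Week 52 | Seen at Week 78 |
|---|---|---|
| Week 6 | 365 − 43 = 322 | 547 − 43 = 504 |
| Week 26 | 365 − 183 = 182 | 547 − 183 = 364 |
| Week 39 | 365 − 274 = 91 | 547 − 274 = 273 |
| Week 52 | – | 547 − 365 = 182 |
| Week 65 | – | 547 − 456 = 91 |

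Stops at these clinic visits give 91 to 504 days. A Day 1 stop seen at Week 78 gives 547 − 1 = 546, and a stop between visits can give only a few days. Each figure is an upper limit on off-drug time at onset, because TEAE status follows onset or worsening, not first report.

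**Other windows.** A completer has 574 − 547 = 27 nominal off-drug days to the Safety Follow-up Visit. With visit windows (± 14 and ± 7 days) the gap can reach 581 − 533 = 48. Under 7.1.10.1 an early terminator has about 0. ET procedures can run 14 + 14 = 28 days past the ET Visit.

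**Illustrative effect on an arm's TEAE percentage.** None of these assumptions is in the documents: constant AE hazard h = −ln(1 − p)/78 per week, where p is the 78-week risk (10%, 30% or 50%); stop times T uniform over 78 weeks; 17% dropout in each arm; full recall at RDO visits; RDO return r of 0 to 1; and, for the between-arm rows, a 5-point dropout imbalance.

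- Mean on-drug risk in dropouts: q = 1 − p/(−ln(1 − p)).
- Mean risk to 4 weeks after stopping: q28 = E[1 − exp(−h × min(T + 4, 78))].
- SAP rule minus 7.1.10.1: 0.17 × r × (p − q).
- SAP rule minus a plain 28-day rule: 0.17 × r × (p − q28).
- Between-arm shift: 0.05 × r × the same bracket.

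| | p = 10% | p = 30% | p = 50% |
|---|---|---|---|
| q | 5.09% | 15.89% | 27.87% |
| q28 | 5.59% | 17.38% | 30.34% |
| SAP minus 7.1.10.1, r = 1 | 0.84 | 2.40 | 3.76 |
| SAP minus 7.1.10.1, r = 0.5 | 0.42 | 1.20 | 1.88 |
| SAP minus 28-day, r = 1 | 0.75 | 2.15 | 3.34 |
| Between-arm shift vs 7.1.10.1, r = 1 | 0.25 | 0.71 | 1.11 |
| Between-arm shift vs 28-day, r = 1 | 0.22 | 0.63 | 0.98 |

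Differences are in percentage points, and all are zero at r = 0. On the same assumptions with full return, off-drug time is 55 × 39 = 2,145 subject-weeks. Of this, 55 × 74²/(2 × 78) = 1,931 (90%) lies more than 28 days after the last dose.

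**The case against.** The strongest reply is that the text largely settles the conflict. Protocol 7.1.10.1 refers the reader to Section 8 for AE definitions, the definition in 8.1.1 is open-ended, and SAP 8.5.2 repeats it. The programmer therefore has a clear rule, and the odd one out is a single clause in 7.1.10.1, which does not say how RDO subjects are treated. Counting every event after first dose is also a legitimate inclusive choice, in line with the treatment-policy handling of discontinuation for efficacy (SAP 8.3.1). Late events can be traced through the by-subject listings (SAP 8.1.1), the RDO listing (SAP 7.1) and the exposure listing (SAP 8.5.1).

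All of this stands, and it keeps the point small. It does not give the tables an off-drug limit, and it does not remove their dependence on an optional visit.

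Three stronger readings are tempting, and the documents do not support them.

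- A reader might infer that ARIA on the ET MRI, or an AE after the ET lumbar puncture, is lost from the tables. That would follow only if 7.1.10.1 governed. Under the open-ended definition both count, and ARIA is in any case analysed from central reads by arm, with shift tables (SAP 8.5.2 and 8.5.3).
- A reader might infer that AE recording or follow-up stops at the ET Visit. It does not. Known AEs and SAEs are followed afterwards (Protocol 5.5, 7.2.14, 8.4.2), and RDO visits collect new ones.
- A reader might take the visit gap as off-drug time at onset, or quote one range of days as the plan's. The gap is only an upper limit, and it varies from a few days to 546.

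**Conclusion.** The point holds as a minor one. The four definitions do not agree on when the TEAE period ends, and those behind the tables have no off-drug limit, so events starting many months after the last dose can be tabulated as treatment-emergent. In practice the period is bounded by the end of AE collection, but for a Week 6 stopper that can still reach Week 78.

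At the planned dropout rate this concerns at most about 55 subjects. Under the assumptions shown, the SAP rule raises an arm's TEAE percentage over 7.1.10.1 by 0 to 3.8 points, and a 5-point dropout imbalance shifts the between-arm difference by 0 to 1.1 points. These are illustrations, not bounds, because return rate, background risk and imbalance are not in the documents. A material bias in the safety comparison should not be inferred. Efficacy analyses and power are unaffected.

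**What to change.** In SAP 8.5.2, before unblinding, define a TEAE as onset or worsening from the first dose through 28 days after the final dose, with these provisions:

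- where the Safety Follow-up Visit after completed treatment falls later, the window runs to that visit;
- for early terminators, the window also covers AEs arising from the protocol's ET MRI and lumbar puncture;
- the window stops at the first extension-study dose if that comes earlier;
- a temporary suspension of drug for an MRI finding (SAP 8.5.3) does not close it.

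Tabulate later-onset AEs, including those from RDO visits, by arm in a separate post-treatment table.

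The first two provisions are needed because a plain 28-day cut would drop some Safety Follow-up events (gap up to 48 days). It would also miss events after a permitted late lumbar puncture, since the 28 days for ET procedures run from the ET Visit, not from the last dose.

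The cost is one definition and one more table. The last dose date is already needed for SAP 8.5.1, and no AE is dropped. No extra contact is needed, and with enrollment complete (SAP 4.1) one might reach few subjects. The downsides are that 28 days is a conventional cut, not derived from pharmacokinetics (it matches the pregnancy-reporting window in Protocol 8.4.3), and that TEAE counts will be slightly lower than under the current SAP rule.
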